12. STATISTICAL CONSIDERATIONS

12.1 Sample size

12.1.1 Primary Efficacy objective:

The primary efficacy endpoint is the relative duration of time where SpO₂ remains between 92 and 96% (inclusive). This will be obtained from continuously monitoring the subjects SpO₂ level throughout the study period such that at least 12 hours of monitoring data are available for each subject. The difference in the average amount of time will be the basis for the efficacy outcome comparison between the two ventilatory strategies.

To assess power for this objective the sample size calculation is based on preliminary data estimating the relative duration of time that SpO₂ remains between 92 and 96% (inclusive). To determine the noninferiority margin, the guidelines provided by FDA were followed (<http://www.fda.gov/downloads/drugs/guidancecomplianceregulatoryinformation/guidances/ucm202140.pdf>). From our preliminary data, the relative duration of time in which the SpO₂ remained between 92 and 96% in a four hour time interval for the MC group was 0.30 with 95% CI (0.23, 0.38). Following the guideline mentioned above we used half of the lower confidence bound to be the margin of non-inferiority (i.e. 0.12, which is equivalent to 7.2 minutes per hour) From our preliminary data, the SD for the MC and PCLC group was 0.33 and 0.23 respectively. Assuming a noninferiority margin of 0.12, a sample size of 91 subjects per group will achieve 80% power with a 2.5% one-sided significant level when the true difference between the group means is assumed to be zero. Allowing a 15% attrition rate for potential withdrawal of subjects the required sample size is 105 per group.

12.1.2 Primary Safety objective:

The primary safety endpoint is the relative duration of time with SpO₂ <88% over the study period. This will be observed by continuously monitoring each subject's SpO₂ level throughout the study period such that at least 12 hours of monitoring data are available for each subject. From our preliminary data the observed relative time where SpO₂ <88% was 0.004 and 0.002 for the MC and PCLC group respectively. The proposed sample size of 105 per group will allow us to conclude non-inferiority with a margin of 0.004 (which is equivalent to 15 seconds/hr) with 95% power with a 2.5% one-sided significant level.

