
For the analysis of secondary safety outcome, data point estimates will be reported with 95% confidence intervals followed by a Fisher's Exact Test at the 5% level of confidence. Specifically the percentage of subjects reporting at least one adverse event (i.e serious, any device related, etc.) will be calculated for each group and compared using Fisher's Exact Test. The relative risk of each adverse event with the corresponding two-sided 95% confidence interval will be presented.

Missing data: The primary analysis is an intent to treat analysis. In order to minimize the possibility of missing data, the total duration of monitoring will be extended for each subject as needed in order to collect at least 12 hours of evaluable data. As a sensitivity analysis, the primary outcome measure also will be calculated as the relative time the subject was on target compared to the total amount of time they were on manual or closed-loop control. Therefore each subject should have the outcome measurement. The amount of missing data is expected

to be low based on past experience with subject retention. However there is a very low probability that some subjects may die before completing 12 hours of monitoring on the device. In this case, the relative duration will be derived by using the total duration of time the subject was on target relative to the monitoring time until they died. If a subject does not have 12 hours of monitoring data on the device due to a reason other than death, we will conduct sensitivity analysis by assuming different scenarios. In a worst case scenario, the primary outcome will be computed as the total time in the target range divided by 720 minutes. In a best case scenario, the primary outcome will be computed as the total time in the target range divided by the total amount of time the subject was observed (i.e. <720 minutes). In the event of missing data on the primary safety and efficacy outcomes (except where the subject died), the reason for the missing values will be explored, and the pattern of missing values (e.g. missing at random, missing completely at random) will be evaluated. In addition, analyses excluding those subjects without 12 hours of monitoring will also be conducted as sensitivity analyses.

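### The plan's worst-case missing-data scenario treats both arms alike, omits deaths and is not written for safety, so it does not bound the PCLC minus MC non-inferiority comparison

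*Combined protocol and SAP*

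**What the plan says.** Section 12.2 (Statistical Analysis) expresses each primary outcome as a proportion of actual monitoring time. It tests non-inferiority with a one-sided lower 97.5% confidence limit, on PCLC minus MC for effectiveness, against a margin of 0.12 for effectiveness and 0.004 for safety. Its missing-data text then sets these rules:

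- **Deaths before 12 hours** are scored by the "total duration of time the subject was on target relative to the monitoring time until they died".
- **Shortfalls for any reason other than death** get two scenarios. The unfavourable one reads: "In a worst case scenario, the primary outcome will be computed as the total time in the target range divided by 720 minutes". The favourable one divides by the time actually observed. Neither differs by arm.
- **Reasons for and patterns of missingness** are explored with deaths again set aside: "In the event of missing data on the primary safety and efficacy outcomes (except where the subject died"). This is a descriptive step, not a scoring rule.
- **Other sensitivity analyses** use time on manual or closed-loop control as the denominator, or drop subjects without 12 hours of monitoring.

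The safety variable is defined in two directions. Sections 4.1.3, 9.1.1 and 12.1.2 use time below 88%. The Protocol Summary uses time at or above 88%, and the analysis text in 12.2 uses time above 88%. The Protocol Summary also divides both primary outcomes by 720 minutes, whereas 12.2 divides by actual monitoring time.

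**The concern.** A worst case should ask how far the unobserved minutes could move the result against the claim being made. Here the claim is that PCLC is not worse than MC, so the unfavourable direction is low scores in PCLC and high scores in MC. The plan's scenario lowers scores in both arms. It applies the unfavourable assumption in PCLC and then largely cancels it by applying the same assumption in MC.

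Two further gaps follow. A death keeps a formula of the same form as the plan's own favourable scenario, and no analysis that retains the subject varies it. And the unfavourable scenario is worded only for the target range, which is the effectiveness outcome, so safety has no stated stress test.

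Non-inferiority on both endpoints is required for study success (Protocol Summary). Early stops may also be informative, because Section 5.6.2 lets the investigator end participation for an adverse event or other medical condition. A reader shown that the result survived the worst case would take more reassurance than the analysis can give.

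**Working it through.** **Inputs from Section 12.1.** SDs: "the SD for the MC and PCLC group was 0.33 and 0.23 respectively". MC mean: 0.30. Margin, power and level: "Assuming a noninferiority margin of 0.12, a sample size of 91 subjects per group will achieve 80% power with a 2.5% one-sided significant level". Assumed true difference: 0. Attrition: "Allowing a 15% attrition rate for potential withdrawal of subjects the required sample size is 105 per group".

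**1. The plan's own figure.** Normal approximation: n = (1.96 + 0.8416)² × (0.33² + 0.23²) / 0.12² = 7.849 × 0.1618 / 0.0144 = 88.2, so 89 per group. A noncentral-t calculation gives 80.8% power at n = 91. The stated 91 is reproduced to within 2, so the inputs are sound for what follows. The 105 is 91 × 1.15 = 104.65, rounded up.

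**2. Assumptions for the illustration.** The documents do not say how many subjects will stop early or when. I take k = 14 non-completers per arm (105 - 91, the plan's own allowance), n = 105 per arm, both means 0.30, SDs unchanged, the untransformed scale, and a fraction f of the 720 minutes unobserved, with f from 0.25 to 0.75. SE = √(0.1618 / 105) = 0.0393. With no true difference, the lower limit on observed-time scoring is -1.96 × 0.0393 = -0.077.

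**3. The planned worst case.** Each non-completer falls from 0.30 to 0.30(1 - f).

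- 14 in each arm: the shifts cancel and the lower limit stays at -0.077 for every f.
- 14 in MC, none in PCLC: the difference moves by +(14/105) × 0.30f = +0.010, +0.020 or +0.030 for f = 0.25, 0.50, 0.75, in PCLC's favour.
- 14 in PCLC, none in MC: the same amounts against PCLC.

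**4. A directional bound.** Unobserved time is off target in PCLC (change -0.30f) and on target in MC (change +0.70f). The difference moves by -(14/105) × (0.30f + 0.70f) = -0.1333f.

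| f | Shift | Lower limit | Against -0.12 |
|---|---|---|---|
| 0.25 | -0.033 | -0.110 | met |
| 0.50 | -0.067 | -0.144 | not met |
| 0.75 | -0.100 | -0.177 | not met |

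The bound crosses -0.12 when k exceeds (0.12 - 0.0769) × 105 / f, that is, from 19, 10 or 7 non-completers per arm at f = 0.25, 0.50 or 0.75. The planned scenario returns the same answer in all of these cases.

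**5. Deaths and effectiveness.** A PCLC subject who dies at 360 minutes with 108 minutes on target scores 108/360 = 0.30 under the plan. Dividing by 720 gives 0.15, a shift of 0.15/105 = 0.0014. Scoring zero gives 0.30/105 = 0.0029. Both are small beside 0.12.

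**6. Safety under a 720-minute denominator.** Take 360 minutes observed, 6 of them below 88%.

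- As time below 88%: 6/360 = 0.0167 becomes 6/720 = 0.0083, which looks better.
- As time at or above 88%: 354/360 = 0.983 becomes 354/720 = 0.492, which looks much worse. This moves the arm mean by (0.983 - 0.492)/105 = 0.0047, more than the 0.004 margin. If the subject is in MC, that movement favours PCLC.

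On observed time the two definitions sum to 1 and the choice is immaterial. With incomplete data over 720 they do not, and the scenario's direction reverses.

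**The case against.** The plan takes real steps against missing data. Monitoring is extended to reach 12 evaluable hours, with collection of up to 24 hours (Section 5.5). Patients with anticipated survival under 48 hours are excluded (5.4), and 12.2 expects few missing data and very few deaths. Deaths are serious adverse events, compared by arm and reviewed by the DSMB, so they are not hidden. Scoring a ventilator-control outcome over time alive is defensible. The 720-minute rule is not useless either: it does penalise PCLC when PCLC loses more subjects. All of this stands, and it limits the size of the point. None of it makes a symmetric rule a bound for a difference.

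Three stronger readings are tempting, and the documents do not support them.

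- A reader might infer that the worst case flatters the safety result. The rule is written only for the target range. If it were carried over, it would flatter time below 88% but worsen time at or above 88%, which is the direction used in the analysis text.
- A reader might infer that deaths keep the favourable score in every analysis. The planned exclusion of subjects without 12 hours would drop early deaths, so this is true only of analyses that retain the subject.
- A reader might infer that one or two deaths could decide the safety result. Counting 11 unobserved hours of one PCLC subject as below 88% does move the arm mean by (660/720)/105 = 0.0087. That shift comes from the imputation, not from the planned primary analysis.

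**Conclusion.** The point holds for the sensitivity analysis, not for the primary rule. The planned worst case does not bound the effectiveness comparison: it changes nothing when non-completion is balanced, and helps PCLC when MC loses more. Under the assumptions in the working, it leaves the lower limit at -0.077 where a directional bound runs from -0.110 to -0.177, crossing -0.12 from 10 non-completers per arm at half the time unobserved. The counts and fractions are assumed; if few subjects fall short of 12 hours, the gap is small.

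The omission of deaths is a gap in the design of the scenario, but has little numerical effect on effectiveness. For safety, no worst case is written, and none can be read unambiguously until the two definitions and the two denominators are reconciled. This is a cheap improvement worth making before the data are analysed, not a defect that invalidates the primary analysis.

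**What to change.** 1. Keep the primary scoring rule, including time alive for deaths.
2. Reconcile the safety definition (below 88%, or at or above 88%) and the denominator (720 minutes or actual monitoring time) across the Protocol Summary and Sections 4.1.3, 9.1.1, 12.1.2 and 12.2.
3. Replace the symmetric worst case with a directional one for both primary endpoints. Score unobserved minutes up to 720 as off target and below 88% in PCLC, and as on target and at or above 88% in MC. Run it with and without the time after death.
4. Add a tipping-point analysis that varies the fraction of unobserved time scored this way, and report where each conclusion changes.
5. Report deaths within the monitoring window by arm beside both primary results.

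The cost is SAP wording and an extra table. The downside is that the extreme safety bound will fail with very little missing PCLC time: 0.004 × 105 × 720 = 302 subject-minutes equals the whole margin, before any allowance for sampling error. The tipping-point result must therefore carry the interpretation, and the SAP should say so in advance.

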12.2 Statistical Analysis

For the primary outcomes, the intent-to-treat (ITT) population will be used for all efficacy and safety analyses. All subjects that were randomized and started the assigned ventilation strategy protocol will be included in the ITT. All summary tables for quantitative parameters will display mean, standard deviation, median, interquartile range, and range (minimum and maximum), as well as number of missing data (if relevant). All summary tables for qualitative parameters will display counts, percentages and number of missing data if relevant. Baseline characteristics will be described using the ITT population. Demographics, medical history and other baseline variables will be summarized as appropriate to the type of data. The primary effectiveness outcome will be defined as the proportion of time during the 12 hour monitoring period that the subject's SpO₂ levels were within the target range relative to the actual total monitoring time (which is targeted to be 12 hours for all subjects). By using the proportion of time instead of the actual time, we are able to normalize the outcome based on the total amount of monitoring time available. We will assess normality of the response variables within each of the two groups by visual inspection of the histograms and box plots and by performing the test for normality of data using the Shapiro Wilk test. If the assumption of normality for the primary effectiveness outcome does not seem tenable, we will use the arcsine square root transformation which is recommended to normalize skewed percentage data. A one-sided lower 97.5% confidence interval will be calculated for the difference between the two monitoring strategy groups (PCLC minus MC) in terms of the effectiveness outcome (duration where SpO₂ remains between 92 and 96% relative to the total monitoring time) and the lower limit will be compared to the noninferiority margin of 0.12. Similar analyses will be conducted for the secondary effectiveness outcome with the only difference being the way the duration is calculated for the secondary effectiveness outcome. For this analysis, the target duration will be calculated as amount of time that SpO₂ remains between 92 and 96% when FiO₂ > 21% and SpO₂ ≥ 92% when FiO₂ = 21%. The safety outcome (duration where SpO₂ remains above 88% relative to the total monitoring time) will be assessed using a one-sided lower 97.5% confidence interval and the lower limit will be compared to the non-inferiority margin of 0.004. If non-inferiority is established for an endpoint, we will proceed in conducting a superiority test and will compare the lower confidence limit to 0.

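### Under the section 12.2 definition the 'best case' missing-data scenario repeats the primary outcome, and no planned scenario tests whether unobserved manual-control time was better than observed

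*Combined protocol and SAP*

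**What the plan says.** The statistical analysis section (12.2) divides each subject's time in the 92 to 96% range by the time actually monitored: "relative to the actual total monitoring time (which is targeted to be 12 hours for all subjects"). The stated reason is that "we are able to normalize the outcome based on the total amount of monitoring time available".

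The missing-data paragraph of the same section then sets these rules:

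- Death before 12 hours: "total duration of time the subject was on target relative to the monitoring time until they died".
- Short of 12 hours for another reason, worst case: "In a worst case scenario, the primary outcome will be computed as the total time in the target range divided by 720 minutes".
- Short of 12 hours for another reason, best case: "In a best case scenario, the primary outcome will be computed as the total time in the target range divided by the total amount". That amount is the subject's own observed time, below 720 minutes.
- A further sensitivity analysis: "the relative time the subject was on target compared to the total amount of time they were on manual or closed-loop control".
- A completer analysis that drops subjects without 12 hours, and an exploration of the reasons for and pattern of missing values.

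The protocol summary (section 1, Objectives) gives a different primary denominator: a fixed 720 minutes for every subject.

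**The concern.** A best-case and worst-case pair should bracket the primary result, so that a reader can see how far the unobserved minutes could move it. Here one end of the bracket coincides with the primary. Which end depends on which of the two stated denominators governs.

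The best-case label is also wrong. Dividing by observed time assumes that the unobserved minutes would have run at the observed rate. A favourable bound would count them as in range.

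This matters because the main test is non-inferiority. Missing data threaten the conclusion if manual control would have done better in its unobserved time than in its observed time, since that would make closed-loop control look relatively better than it was. The best case was the natural place to test this, and as written it cannot.

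**Working it through.** **The plan's own figure.** Inputs from section 12.1.1 are SDs of 0.33 (manual) and 0.23 (closed-loop), margin 0.12, one-sided 2.5%, 80% power and true difference zero. The normal approximation gives n = (1.96 + 0.842)² × (0.33² + 0.23²)/0.12² = 7.85 × 0.1618/0.0144, or 89 per group. A t-based calculation gives 80.8% power at the stated 91. The figure reproduces closely enough and is not in dispute. The plan then allows 15% attrition and enrols 105 per group.

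**The identity.** Let t be minutes in range and T minutes monitored, with T < 720 and the subject alive.

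| Quantity | Formula | T=480, t=240 | T=360, t=108 |
|---|---|---|---|
| Primary, section 12.2 | t/T | 0.500 | 0.300 |
| Planned best case | t/T | 0.500 | 0.300 |
| Planned worst case | t/720 | 0.333 | 0.150 |
| Primary, protocol summary | t/720 | 0.333 | 0.150 |
| All unobserved minutes in range | (t + 720 − T)/720 | 0.667 | 0.650 |

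Subjects who die get t/T in both the section 12.2 primary and the best case, and subjects with full data are not affected. The two analyses therefore agree subject by subject, and the mean difference and confidence limit are identical. Under the protocol summary's definition the coincidence moves to the worst case, for short subjects who did not die. The planned best case then differs from the primary, but it raises values only to the observed rate, so better-than-observed manual-control time is still untested.

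**What the other scenarios do.** I simulated 2,000 trials per scenario with 105 per arm, the plan's SDs, an assumed mean of 0.30 in both arms, short subjects observed for 60 to 700 minutes, and about one fifth of them counted as deaths. The average lower limits, closed-loop minus manual, were:

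- 15% short in the closed-loop arm only: primary −0.076, best case −0.076, worst case −0.093.
- 15% short in the manual arm only: primary −0.077, best case −0.077, worst case −0.058.

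The worst case does move the result. When the short subjects are in the manual arm, it moves it in favour of closed-loop control. The completer analysis also differs from the primary, but it removes subjects and sets no bound on their unobserved time.

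**Hypothetical size of the untested direction.** Suppose a fraction f of manual-control subjects stop at 360 minutes with 108 in range, and all their unobserved minutes are counted as in range. Each value rises by 0.65 − 0.30 = 0.35, so the manual mean rises by 0.35f:

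- f = 5%: 0.35 × 0.05 = 0.0175; 0.0175/0.12 = 15% of the margin.
- f = 15%: 0.35 × 0.15 = 0.0525; 0.0525/0.12 = 44% of the margin.

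With 105 per arm and zero true difference, the expected lower limit is −1.96 × √((0.33² + 0.23²)/105) = −0.077, which leaves 0.043 before −0.12. Holding the SDs fixed, a shift of 0.0525 takes it to about −0.130, past the margin. A shift of 0.0175 takes it to about −0.094, which is not. Crossing begins at f = 0.043/0.35, about 12%.

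**The case against.** A reader might infer that the sensitivity analyses as a whole show nothing about robustness. The documents do not support that. The worst-case and completer analyses differ from the section 12.2 primary, and the plan also explores why data are missing. Only the best case is empty under that definition. The primary estimate, the margin comparison and the error rate are not affected.

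A reader might also infer that the analysis over time on manual or closed-loop control is another duplicate and should go. That does not follow. Loss of the oximetry signal pauses closed-loop control (section 3.1.1). Clinicians may override it, and procedures at FiO₂ 1.0 and time outside the ICU are excluded from analysis (both section 4.3). Time on control can therefore differ from monitoring time. What is missing is a definition of that denominator.

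The redundancy is partly a consequence of the two conflicting primary denominators. This is fair, but settling the denominator alone only moves the duplication to the other scenario.

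The 44% figure should not be read as a forecast. It puts all the shortfall in one arm, stops every such subject halfway and counts every unobserved minute as in range, against a manual-control estimate of 0.30 (95% CI 0.23 to 0.38) in section 12.1.1. The 15% is a withdrawal allowance for both groups. The plan expects few missing data and extends monitoring to reach 12 evaluable hours, with up to 24 hours of collection (section 5.5). Section 3.2.2 also reports more time in range under automated control in the prior trial, which would leave more room than a zero difference does. These points limit the likely size. They do not supply the missing test, which should be set in advance without relying on a favourable result.

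**Conclusion.** The point holds in limited form. Under the section 12.2 definition the best case equals the primary for every subject and is not a favourable bound. Under the protocol summary's definition the worst case repeats the primary for short subjects who did not die. This reads time observed and actual monitoring time as the same quantity, since the documents define no difference between them.

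Under either definition, no planned scenario tests whether unobserved manual-control time was better than observed, and the common worst case can favour closed-loop control. The hypothetical shift is 0.0175 to 0.0525 for 5% to 15% of manual-control subjects stopping halfway; the planned best case shows none. If few subjects fall short, the practical effect will be small. The change should be made, but it concerns a supplementary analysis and does not undermine the primary one.

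**What to change.** 1. State one primary denominator and use it in both the protocol summary and section 12.2. If 720 minutes is chosen, say that the worst case is then the primary for short subjects who did not die.
2. For subjects short of 12 hours for a reason other than death, redefine the best case as (in-range + unobserved minutes)/720. With the existing t/720 this gives a genuine range under either denominator.
3. Add an arm-specific stress test of non-inferiority: unobserved manual-control minutes counted as in range, against closed-loop subjects at their primary value. A more adverse version also counts unobserved closed-loop minutes as out of range.
4. Keep the analysis over time on manual or closed-loop control, and state how its denominator treats overrides, signal loss and excluded periods.

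The cost is about a paragraph of SAP text and a few lines of code, with no new data. The downside is one more supplementary analysis whose bound is deliberately extreme; the report should say so, so that crossing the margin there is not read as failure of the primary test.
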